procedures, consults, medications, lab values, and culture results leading up to and after the fat grafting procedure. Pre-procedure blood tests, including but not limited to blood clotting, red blood cell count, electrolytes, and cultures, history/physical exams of the body (especially the affected limb), MRI and CT scans, menstrual status and/or results of pregnancy testing, and any medical information that could adversely impact the outcome of the fat grafting procedure. This research study will result in identifiable information that will be placed into the subjects medical records held at UPMC. The nature of the identifiable information resulting from the subject's participation in the this research study that will be recorded in their medical record will be derived from the fat grafting procedure as detailed above. Psychiatric interview information will be entered into the medical record only if it is important to ensure the subject's medical or physical safety.

- 2.14.1 Will protected health information from a non-UPMC/Pitt HIPAA covered entity be obtained for research purposes or will research data be placed in the non-UPMC/Pitt medical record? * Yes

If Yes, describe how the HIPAA requirements will be met:If the subject is coming from an outside entity, other than a UPMC covered entity, and the patient's medical records accompany the potential subject or be voluntarily sent in anticipation of the visit for the Principal Investigator's screening evaluation. We will look at all records that are provided appropriate to the study and may include the following: all information pertaining to the trauma event and surrounding surgical and medical procedures, prior procedure blood tests (including but not limited to complete blood count (CBC) with Differential and Platelets, comprehensive chemistry panel, urinalysis, and culture results) operative notes, physical therapy assessments, consultations, prosthetic/orthotics evaluation/ history, CT, MRI scans, EKG, Chest X-rays, history and physical exams, and any other information pertaining to the affected injury, limb trauma that could directly affect the outcome of the proposed surgical procedure. Research data will not be placed in non-UPMC/Pitt medical records.

I, [name] , certify that any member of my research team accessing, reviewing and/or recording information from medical records have completed the CITI Privacy & Information Security course or, if completed within the past year, the Internet-Based Studies in Education and Research (ISER) HIPAA for Researchers (Formerly RPF Module 6). The HIPAA certificates must be available for review if audited but do not need to be uploaded into this OSIRIS application.

* Yes

- 2.14.2 Are you requesting a waiver of the requirement to obtain written HIPAA authorization for the collection of the PHI?* No

[reviewer notes-]

Section 2 - Research Design and Methods

2.15 Does this research study involve the long-term storage (banking) of biological specimens?

* No

2.15.1 Broadly describe the intended future use of the banked biological specimens:

2.15.2 Indicate the planned length of storage of the banked biological specimens:

*

2.15.3 Will biological specimens be stored without identifiers or linkage codes? *

[reviewer notes-]

Section 2 - Research Design and Methods

2.16 Will research participants be asked to provide information about their family members or acquaintances?

* No

2.16.1 Describe what information about the third party will be obtained from the participant:

2.16.2 If the information about the third party is of a private nature, can the identity of the third party be readily ascertained or associated with this information?

*

Describe the private information that will be collected and recorded about the third party:

[reviewer notes-]

Section 2 - Research Design and Methods

Section: Section 2 - Research Design and Methods

2.17

What are the main outcome variables that will be evaluated in this study?

Primary outcomes: Improvement of pain at the amputation site, improved ability to tolerate a prosthesis, and generation of a stable volume of adipose tissue at the amputation site (as measured by clinical assessment by rehabilitation sciences and prosthetics team, quality of life measures, and high resolution imaging). This will be compared between the standard fat grafting group (n=15) and the adipose cell enriched fat grafting group (n=15). Secondary outcomes: Local and systemic complications resulting from fat graft procedure (infection, fat necrosis, hematoma, seroma); basic assays of adipose cell behavior to elucidate the functional properties of adipose cells used for grafting, with correlation to outcomes.

2.18

Describe the statistical approaches that will be used to analyze the study data.

* Addressed below:

Pain and Serial computed tomography imaging will be performed and measured as parametric data sets before fat grafting and afterwards at various time points using a paired t-test model. Repeated measures analysis of variance will be used to evaluate change over time in all outcome measures. Using standard conventions of alpha=0.05 and beta=0.8, an enrollment of thirty patients may provide sufficient power to detect a Cohen's effect size of about 0.9 which is anticipated to be adequate for detecting clinically meaningful differences in the volume of soft tissue. A composite functional score will be constructed from the prosthetics and occupational therapy evaluations and compared between study groups. The details of this analysis, including which evaluations will be included in the score and relative weight, can be best determined as the study progresses and initial data sets are acquired. Additionally, each assessment score from the specific tests will also be considered individually for comparison.

[reviewer notes-]

Section 2 - Research Design and Methods

2.19

Will this research be conducted in (a) a foreign country and/or (b) at a site (e.g., Navajo Nation) where the cultural background of the subject population differs substantially from that of Pittsburgh and its surrounding communities?* No

Note that copies of training records, licenses, certificates should be maintained in the study regulatory binder and are subject to audit by the Research Conduct and Compliance Office (RCCO).

Section: Section 2 - Research Design and Methods

In addition, individuals planning to conduct human subject research outside the United States must complete an optional module on the CITI training website: International Studies. Click [here](#) to access the instruction sheet for accessing optional CITI modules.

- 2.19.1 Address the following for each of the foreign/culturally different sites where this research will be conducted:
- Name of site
 - Name of authorized individual (e.g., IRB Chair) from the local IRB or other human subject protections entity that is responsible for the review and approval of the project; upload approval letter with an English translation, if applicable
 - Name and qualifications of the site collaborator responsible for the conduct of the research (e.g., site PI)
 - The anticipated number of subjects that will be enrolled at that site
 - If Federally funded, provide the Federalwide Assurance number (FWA) assigned to the site *

| Site | Date Modified |
|------|---------------|
|------|---------------|

There are no items to display

- 2.19.1.1 Provide a description of the context of cultural norms and local laws and highlight differences between U.S. culture in all areas relevant to your study, including, at a minimum:

- Age of majority of participants to be enrolled
- If study includes minors or decisionally impaired subjects, summarize laws on guardianship
- If your study involves any invasive medical procedure (including blood draws), provide assurance that the individuals undertaking those procedures for research purposes are appropriately credentialed.
- If your study involves the administration of a drug, device or biologic for research purposes, describe the process for shipping, labeling, storing and dispensing, and indicate how these are consistent with all relevant local (and US) laws, including those requiring import / export permits.
- If your study involves collection of biological specimens, describe the process for shipping, labeling, storing and using such samples. Identify any special local consent requirements, and any special permits that may be required by local law.

*

- 2.19.1.2 Describe any aspects of the local cultural, political or economic climate that might increase the risks of harm for either local participants or researchers. Describe the steps you will take to minimize these risks. UPitt Faculty, Staff, and Students must access the Travel Registry page. Go to [my.pitt.edu](#) and the link is displayed under My Resources.

*

- 2.19.2 Will all individuals being recruited to participate in this research study be able to read and comprehend English*

Section: Section 2 - Research Design and Methods

If No, describe how consent will be obtained. Explain provisions for culturally appropriate recruitment and consent accommodations such as, translations or involvement of native language speakers, especially if literacy is not widespread in this country.

- 2.19.2.1 If translated documents are used, upload a signed translator certification form and back translations (if applicable):(Translator Certification Form is available under the Resources tab located to right of this item)

Name Modified Date

There are no items to display

- 2.19.3 Will all of the research procedures described in this IRB application be conducted at the foreign/culturally different sites?

* Yes No

If No, describe the subset of research procedures to be performed at the sites:

- 2.19.4 To what extent do the local site requirements to protect subject confidentiality and privacy differ from US standards. If applicable, explain how those will be addressed by this research team:*

- 2.19.5 If the researcher is a student, describe how the student will communicate with the advisor during the conduct of the research and how the advisor will oversee the research:

[reviewer notes-]

Section 2 - Research Design and Methods

- 2.21 Will this research study be conducted within a nursing home located in Pennsylvania?

* No

- 2.21.1 Does this research involve a medical procedure or an experimental treatment?*

Section: Section 2 - Research Design and Methods

- 2.21.2 Does the research study involve the exposure of nursing home residents to pain, injury, invasion of privacy, or ask the resident to surrender autonomy?

*

If Yes to either question, upload the Pennsylvania Department of Health approval letter. 28 PA Code Section 201.29 (o) specifies that prior to the initiation of research, and in addition to IRB approval, any study that includes experimental research or treatment conducted in a nursing home must be approved by the Pennsylvania Department of Health. A signed consent form from nursing home resident-subject is also required.

Name Modified Date

Section: Section 3 - Human Subjects

[reviewer notes-]

Section 3 - Human Subjects

- 3.1 What is the age range of the subject population? 18 years of age and older.
- 3.2 What is their gender?* Both males and females Provide a justification if single gender selected:
- 3.3 Will any racial or ethnic subgroups be explicitly excluded from participation?* No If Yes, identify subgroups and provide a justification:
- 3.4 For studies conducted in the U.S., do you expect that all subjects will be able to comprehend English?

* Yes

If No, identify what languages will be understood by subjects and describe your plan to manage communication with non-English speaking subjects during all phases of the study:

- 3.4.1 If translated documents are used, upload a signed translator certification form and back translations (if applicable):

Name Modified Date

There are no items to display

[reviewer notes-]

Section 3 - Human Subjects

3.5 Participation of Children: Will children less than 18 years of age be studied?* No

If No, provide a justification for excluding children: Our target population for this study is military and civilian, who are restricted to age 18 years and above. Children will be excluded because any active growth surrounding an amputation site will obscure our ability to detect changes due to the surgical procedure over time.

3.5.1 Specify the age range of the children to be studied. (Check all that apply below:)

*

Choices

There are no items to display

3.5.2 Provide a rationale for the specific age ranges of the children to be studied:

3.5.3 Describe the expertise of the study team for conducting research with children within this age range:

3.5.3.1 Have you obtained the following clearances from all research staff who may have direct contact with children under the age of 18? Direct contact under the law includes face-to-face, and telephonic or electronic, contact with minors. Please see the Child Clearances guidance document for further explanation?

Pennsylvania Department of Public Welfare Child Abuse History Clearance; Pennsylvania State Police Criminal Record Check; and FBI Criminal Background Check

Note: If No, once all clearances are obtained, a modification must be submitted. If you selected N/A, please explain:

It is important to note that "direct contact" refers not only to face-to-face meetings but also extends to communication via phone (including text messaging), social media or internet. Direct contact also includes the care, guidance, supervision or control, or

routine interaction with, minors. Conversely, a participating investigator or support staff member who does not have direct contact, either electronically or in person, with children does not need to obtain clearances (e.g., statistician, non-clinical laboratory personnel, etc.). If your research study provides babysitting services, the babysitters must have the required child clearances. * Note: It is the responsibility of the principal investigator to ensure that all research staff have these clearances prior to any interaction with children. Contact Human Resources at [contact] for assistance with this process.

3.5.4 Describe the adequacy of the research facilities to accommodate children within this age range:*

3.5.5 Permitted Categories of Research: The Federal Policy and FDA regulations governing human subject protections specify that research involving children must fall into one of the following permitted categories.

*

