- 3.11 Identify each of the disease or condition specific subgroups (include healthy volunteers, if applicable) that will be studied.
- Click on the "Add" button and specify for each subgroup:
- 1) how many subjects will undergo research related procedures at this site; and
 - 2) if applicable, how many subjects will be required to undergo screening procedures (e.g., blood work, EKG, x-rays, etc.) to establish eligibility. Do Not include subjects who will undergo preliminary telephone screening.*

| | Subgroup | Number to undergo research procedures | Number to undergo screening procedures |
|------|--|---------------------------------------|--|
| View | amputees receiving TGI cell enriched processing fat grafting | 15 | 35 |
| View | amputees receiving standard fat grafting | 15 | 35 |

There are no items to display

- 3.12 Provide a statistical justification for the total number of subjects to be enrolled into this research study at the multicenter sites or this site.* Described below: The proposed study is designed as a single center, prospective, randomized pilot outcome study to exam the effect of two (2) fat grafting procedures on either upper or lower extremity amputations. The major endpoint is pain at the amputation site and the ability to wear prosthesis. To the best of our knowledge, there are no clinical reports that describe quantitatively the change in extremity amputation site pain to fat grafting over time. This is especially true in comparing an upper extremity amputation site [low weight bearing

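### Three primary outcomes share one alpha of 0.05 with no order, split, primary visit or primary contrast, so even one test each gives about a 13% to 14% chance of a false primary result

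*Combined protocol and SAP*

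**What the plan says.** Section 2.17 lists the primary outcomes as "Primary outcomes: Improvement of pain at the amputation site, improved ability to tolerate a prosthesis, and generation of a stable volume of adipose tissue" and says they will be compared between the standard and the cell-enriched arm, 15 patients each.

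Other sections give a different set:
- Abstract (CS2.1), aims, and section 1.2: pain and tolerance of a prosthesis.
- Abstract, study design paragraph: graft retention and tolerance of a prosthesis.
- Section 3.12: "The major endpoint is pain at the amputation site and the ability to wear prosthesis".

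Section 2.18 states alpha once, in the sample-size sentence: "Using standard conventions of alpha=0.05 and beta=0.8, an enrollment of thirty patients may provide sufficient power". The effect size given there is a Cohen's d of about 0.9, and it is tied to soft tissue volume only. For analysis the section plans:
- pain and CT measured "before fat grafting and afterwards at various time points using a paired t-test model";
- repeated-measures ANOVA for change over time in every outcome;
- a composite functional score whose contents and weights are to be settled as data arrive, compared between arms;
- and, in addition, "each assessment score from the specific tests will also be considered individually for comparison".

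No section gives an order of testing, an alpha split, a primary visit, a primary between-arm contrast or a rule for declaring success.

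**The concern.** A stated alpha of 0.05 normally tells the reader how often the trial would report a primary effect that is not there. With three primary outcomes and no rule joining them, 0.05 describes each test, not the trial. Because the primary set changes between sections, a reader also cannot tell which result decides the trial.

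This matters because section 1.4 presents the study as validating the technique, and section 2.3 describes it as non-blinded. If one of the three outcomes were significant at one visit, nothing in the plan would stop it from being reported as a positive primary finding, or show that it had been chosen in advance.

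**Working it through.** **1. The plan's own figure.** Inputs from 2.18: 30 patients (15 per arm), alpha 0.05, d about 0.9. The stated beta of 0.8 is read as power of 0.8. The plan does not say whether the test is one- or two-sided.

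Patients per arm = 2(z for alpha + z for power)²/d².
- One-sided: 2(1.645 + 0.842)²/0.81 = 15.3, so 16 per arm (32 in total). Power with 15 per arm is 79.4% (normal) or 77.6% (t).
- Two-sided: 2(1.960 + 0.842)²/0.81 = 19.4, so 20 per arm. Power with 15 per arm is 69.3% (normal) or 66.3% (t).

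The figure therefore reproduces, within two patients, for one one-sided test of one outcome. The sentence attaches it to soft tissue volume. It makes no allowance for a second or third primary outcome.

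**2. One between-arm test per outcome.** With k independent tests at 0.05 and no true effect, P(at least one false positive) = 1 − 0.95^k.
- Two outcomes (as in 1.2, 3.12 or the abstract's study design): 1 − 0.9025 = 9.75%.
- Three outcomes (2.17): 1 − 0.857 = 14.3%.

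The documents give no correlations between outcomes, so these are assumed. The simulation used 15 v 15, normal data, two-sided t-tests at 0.05 and 40,000 null trials per setting:

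| Assumed correlation between the three outcomes | P(at least one false positive) |
|---|---|
| 0 | 14.2% (exact 14.3%) |
| 0.3 | 13.7% |
| 0.5 | 12.5% (12.9% in a separate run) |
| 0.7 | 11.0% |
| 0.9 | 8.3% |

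**3. A scenario with visit-by-visit tests.** Section 2.7 schedules pain at six post-operative visits (POV1 to POV6), and imaging and the prosthetic assessments at three each (POV4 to POV6). Comparing the arms at each would give 6 + 3 + 3 = 12 tests.
- Independent: 1 − 0.95^12 = 46.0%.
- Correlation 0.5 between visits, 0 between outcomes: about 39%.
- Correlation 0.5 and 0.5: about 33%.
- Correlation 0.8 between visits, 0.5 between outcomes: about 26%.

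The test count and the correlations in this step are assumptions.

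**4. What a remedy does.**
- A Bonferroni split over three outcomes (0.05/3 = 0.0167 each) gives 1 − (1 − 0.0167)³ = 4.9% if independent, and at most 5% otherwise. Two-sided power at d = 0.9 with 15 per arm falls from about 66% to about 48% (t).
- A fixed order keeps the overall rate at 5% or below and leaves the first outcome its full 0.05. If d = 0.9 held for all three outcomes and they were independent, the third would be reached and found significant with probability about 0.663³ = 0.29.

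**The case against.** The strongest reply is that this is a 30-patient pilot. The title, 2.3 and 3.12 all call it one, 2.18 says only that 30 patients may give sufficient power, and the documents never claim a trial-wide 5% error rate. On that view strict control is partly a preference. That stands in part: an estimation-only analysis would answer the point fully, but the plan does not declare one. It cites alpha and power, says in 3.12 that the randomization scheme preserves statistical rigor for testing, and in 1.4 speaks of validating the technique.

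Second, correlation lowers the figure. Section 2.5.1 lists excessive pain among the ways intolerability shows itself, so pain and tolerance could be strongly correlated. That is fair, and it is why the result at 0.9 is shown. Even there it is about 8%, above 5%.

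Third, a reader might infer that the arms are to be tested at every visit, each at 0.05, so that the error rate is as high as 39% or more, and that any one significant result would count as success. The documents do not support this. The t-test at various time points is a paired, within-patient before/after test named only for pain and CT. Repeated-measures ANOVA can yield a single test per outcome. Alpha appears only in the sample-size sentence, so 0.05 for every comparison is an inference, and there is no success rule of any kind. Nor is the count of twelve firm: 2.7 adds a telephone pain report at 18 months, and says that which prosthetic assessments are done depends on the limb. The visit-by-visit range is therefore a scenario, not a property of the plan.

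**Conclusion.** The point holds in a limited form. Section 2.17 names three primary outcomes for a two-arm comparison, 2.18 supplies one alpha without order, split, visit or contrast, and the sections disagree on which outcomes are primary. With one two-sided between-arm test per outcome at 0.05, the chance of at least one false primary result is about 13% to 14%, assuming correlations of 0.5 to 0, and about 8% at 0.9. Reading the ANOVA as one test per outcome does not remove this, because the figure already assumes a single test each. The larger range, roughly 26% to 46%, applies only if the arms are also compared at each scheduled visit, which the plan does not say.

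**What to change.** 1. Reconcile the primary-outcome statements in the abstract, 1.2, 2.17 and 3.12.
2. In 2.17 and 2.18, name one between-arm contrast at one visit where all three outcomes are measured (POV4, POV5 or POV6), and state whether the test is one- or two-sided.
3. State a fixed testing order before any outcome data are seen, with each outcome tested at the full 0.05 only if the one before it is significant. Pain, then tolerance, then volume follows the listing in 2.17 and the pain-then-prosthesis order in 1.2 and 3.12. The sponsor should confirm it, because 2.18 ties the power statement to volume and the abstract's study design lists retention first.
4. Define the tolerance measure in advance, for upper and lower limbs. Section 2.5.1 says that no validated instrument for intolerability exists, and 2.18 leaves the composite open. A sequence cannot pass through an undefined test.
5. Report all other visits and individual scores with 95% confidence intervals and no significance claims.

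This needs no extra patients. The text on order and visit is a few sentences; settling the tolerance measure is the larger task. The downside is that later outcomes can be claimed as significant only if the earlier ones are.

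If the pilot is meant for estimation only, say so in 2.18 and drop the significance claims. Steps 1 and 4 are still needed.
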